### **Myocardial Glucose Uptake: F-2-deoxyglucose/PET**

The same 19 diabetic subjects who received the  $\beta$ -OH-B infusion designed to raise the plasma  $\beta$ -OH-B concentration by 2 mmol/L (Group II) will receive a cardiac positron emission tomography (PET) study to examine the effect of hyperketonemia on myocardial glucose uptake and blood flow. The PET study will be performed with subjects lying comfortably in the scanner as previously described (19,78,79). Subjects will report to the Research Imaging Institute at 0700 following a 10 hour overnight fast. PET scans will be performed in two-dimensional imaging mode using ECAT 931-08/12 PET scanner (CTI, Knoxville, TN) with 10.5-cm axial field of view and resolution of  $8.4 \times 8.3 \times 6.6$  mm^3 full width at half-maximum. Point-of-care urine pregnancy test will be done for women of reproductive age prior to injection of radioisotopes. A catheter (for arterialized blood withdrawal) is placed in a vein on the dorsum of the hand, which rests in a box heated to 60°C, and three baseline blood samples are drawn at 15 minute intervals. A second catheter for infusion of test substances is inserted into an antecubital vein. Following optimization of subject position, a 20-minute transmission scan will be performed after exposure of a retractable 68Ge ring source to correct emission data for tissue attenuation of gamma photons. Then, O-water (10.5 MBq/kg) is administered intravenously through the catheter over 20 seconds at infusion rate of 10 ml/min and PET scan is performed to measure myocardial blood flow (MBF), as previously described (19,78,79).

At time zero a prime-continuous infusion of  $\beta$ -OH-B (prime = 1.5 mg/kg.min for 20 minutes; continuous infusion = 0.75 mg/kg.min) is started and continued for 380 minutes, and blood samples are drawn approximately every 30 to 60 minutes during the infusion. At 250 minutes to the start of the  $\beta$ -OH-B infusion, a 20-minute transmission scan is performed followed by a repeat cardiac O-water-PET study. At 300 minutes [F]fluoro-2-deoxy-D-glucose (185 MBq) is injected and a dynamic PET scan is performed for measurement of myocardial glucose uptake as previously described (19,78,79). At 360 minutes to the start of the  $\beta$ -OH-B infusion, two consecutive 20-minute dynamic scans of the abdominal and thigh area are performed to measure kidney and skeletal muscle glucose uptake. Urine will be collected before and after the 18F-FDG-PET scan to calculate endogenous glucose production (80). In ~14-30 days subjects will return for a repeat 18F-FDG-PET study with one exception: NaHCO3 will be infused instead of  $\beta$ -OH-B. The two studies will be performed in random order. All radioactive tracers are produced at the on-site cyclotron radiochemistry facility in the RadiolImaging Institute (RII) at the UTHSCSA.

For subjects in Group II, cardiac MRI studies (two study days, one with  $\beta$ -OH-B and other with NaHCO3 infusion) are performed before PET studies. Depending on the scanner availability, however, we may choose to perform PET studies before the cardiac MRI studies.

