**Table 1. Events for subjects in GROUPS I and III:**

Visit	Visit 1	Visit 2
Assessments	Screening	MRI Study 1
Schedule	DAY -30 to -7	Day 0-30
Routine Blood Chemistries, CBC, UA, lipid profile, TSH/ T4, A1c, NT-proBNP, hCG	X	
ECG, DXA, ECHO (if not done within 3-6 months of screening)	X	
Vital signs	X	X
Baseline Cardiac MRI and baseline blood samples $\times$ 3: $\beta$ -OH-butyrate, acetoacetate, glucose, FFA, lactate, pyruvate, glycerol, HCO 3 , insulin/C-pep, glucagon, renin and aldosterone		X
Blood safety monitoring before (3 samples) and after (3 samples) the infusion: glucose, potassium with iSTAT		X
Prime-continuous infusion of $\beta$ -OH-B (0.8 M solution; pH adjusted to 7.24) to increase the plasma $\beta$ -OH-B concentration by GROUP I: ~0.5 mmol/L (6-hrs) GROUP III: ~5.0 mmol/L (3-hrs)		X
Post-infusion Cardiac MRI and blood samples $\times$ 3: NT-proBNP, $\beta$ -OH-butyrate, acetoacetate, glucose, FFA, lactate, pyruvate, glycerol, HCO 3 , insulin/C-pep, glucagon, renin and aldosterone		X

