**Table 2. Events for subjects in GROUP II:**

Visit Assessments Schedule	Visit 1 Screening DAY -30 to -7	Visit 2 MRI Study 1 Day 0-30	Visit 3 MRI Study 2 Day 7-30 after MRI Study 1	Visit 4 PET Study 1 Day 7-30 after MRI Study 2	Visit 5 PET Study 2 Day 7-30 after PET Study 1
Routine Blood Chemistrys, CBC, UA, lipid profile, TSH/T4, A1c, NT-proBNP, hCG	X				
ECG, DXA, ECHO (if not done within 3-6 months of screening)	X				
POC urine pregnancy test				X	X
Vital signs	X	X	X	X	X
Baseline Cardiac MRI and baseline blood samples $\times$ 3: $\beta$ -OH-butyrate, acetoacetate, glucose, FFA, lactate, pyruvate, glycerol, HCO 3 , insulin/C-pep, glucagon, renin and aldosterone		X	X		
Blood safety monitoring before (3 samples) and after (3 samples) the infusion: glucose, potassium with iSTAT		X	X	X	X
6-hour prime-continuous infusion of $\beta$ -OH-B (0.8 M solution; pH adjusted to 7.24) to increase the plasma $\beta$ -OH-		X		X	
6-hour prime-continuous infusion of NaHCO 3 (0.12 M solution); volume to be infused will be the same as $\beta$ -			X		X
Post-infusion Cardiac MRI and blood samples $\times$ 3: NT-proBNP, $\beta$ -OH-butyrate, acetoacetate, glucose, FFA, lactate, pyruvate, glycerol, HCO 3 , insulin/C-pep,		X	X		

18F-2-DOG/15O-H 2 O PET study and blood samples x 12: NT-proBNP, $\beta$ -OH-butyrate, acetoacetate, glucose, FFA, lactate, pyruvate, glycerol, HCO 3 and hematocrit (with iSTAT), insulin/C-pep and glucagon, erythropoietin, urine 18F-radioactivity.				X	X
---	--	--	--	---	---

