**Subjects:** 78 type 2 diabetic subjects with New York Heart Association (NYHA) Class II-III heart failure (75) and ejection fraction less than 45% (documented by patient's medical records with an ECHO or any other heart imaging study) will be studied. Other inclusion criteria include age = 18-80 years; BMI =23-38 kg/m^2; approximately 39 males/39 females; HbA1c = 5.5.0-10.0%; BP < 145/85 mmHg; eGFR > 30 ml/min•1.73 m^2. Subjects must be on a stable dose of guideline-directed heart fail medication (i.e. ACEI, ARB, ARNI, beta blocker, diuretic and/or mineralocorticoid receptor antagonist). Patients must be on stable antihypertensive therapy for at least 2 months. Only diabetic subjects treated with diet/exercise, metformin monotherapy, sulfonylurea monotherapy, low-dose (defined as  $\leq$  45 IU total daily dose) insulin therapy or combination metformin/SU/low-dose insulin therapy. Diabetic subjects treated with a GLP-1 RA or DPP4i (since they inhibit glucagon secretion) or pioglitazone (since it improves skeletal muscle and myocardial insulin sensitivity), SGLT2 inhibitor (since they increase plasma ketone concentration) or high-dose insulin will be excluded. Only subjects whose body weight has been stable ( $\pm$ 4 pounds) over the last 3 months will be studied. Subjects with contraindications for MRI procedures will be excluded, including patients with pacemakers. Women who are pregnant or breastfeeding will be excluded. All subjects with NY Heart Association Class II-III will be recruited from the Heart Failure Clinic at the University of Texas Health Science Center ([name] and [name]). Medical records for Cardiology and Diabetes clinics will be reviewed for eligibility and if potential participants meet inclusion/exclusion criteria they will be contacted about participating in the study. Collectively, these two clinics follow  $\sim$ 4,700 patients who have NYHA Class II-III and approximately 40% of these individuals have type 2 diabetes mellitus. The study will be approved by the UTHSCSA IRB and all subjects will provide written voluntary consent prior to participation.

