**Study Protocol:** Up to 100 Study participants will be asked to fast prior to consenting to the study and the day of the screening visit (day -30 to -7) participants will first sign consent form and eligibility criteria (A1c, eGFR, BP etc) will be confirmed and subjects will undergo a medical history and physical exam to exclude major organ system diseases other than diabetes and cardiac disease. Routine blood chemistries, CBC, urinalysis, lipid profile, TSH/T4, NT-proBNP, and EKG will be obtained. Blood pressure will be measured after reclining for 5 minutes in a quiet room and the mean of three measurements will be recorded. Subjects also will have a DEXA to measure total body fat content. If patient has not had an ECHO within 3-6 months of the screening visit, we will refer patient to the cardiac ECHO to confirm that the EF is < 50% (76).

Within 1-4 weeks after the screening visit, subjects will return to the Research Institute (RI) at 0700 h for a cardiac MRI (19,77) to confirm that the EF is < 50% and to obtain quantitative measures of baseline cardiac functional parameters: chamber volumes and pressures, wall thickness, LV diastolic function (E/A ratio, peak LV filling rate, diastolic volume) and LV systolic function (cardiac output, stroke volume, systolic volume, peak LV ejection rate). Strain and tagging also will be measured. To reduce the likelihood of hypoglycemia during the study procedures, subjects will be asked to withhold their antidiabetic therapy on the day of the studies until they have received a meal at the end of the study days.

Cardiac MRI will be performed by [name]. (Professor, Department of Radiology, UTHSCSA) on 3.0T MRI System (TIM, Trio, Siemens Medical Solution, Malvern, PA) with six channel anterior phased-array torso coil and corresponding coil elements (12 channels total) (19,77). Before cardiac MRI, catheters will be inserted into both antecubital veins for all blood withdrawal and  $\beta$ -OH-B infusion, respectively. Three blood samples will be drawn at 10-15 minute intervals for measurement of NT-proBNP, -OH-butyrate, acetoacetate,

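### After the screening hCG, pregnancy is re-tested only on Group II's two PET days, so no MRI-day infusion has a same-day test

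*Combined protocol and SAP*

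**What the plan says.** The Subjects paragraph under Experimental Design states the exclusion without limiting it to a group or procedure: "Women who are pregnant or breastfeeding will be excluded". The same paragraph sets the age range ("Other inclusion criteria include age = 18-80 years") and the planned sex split ("approximately 39 males/39 females"). It does not restrict women to those who are post-menopausal or sterile.

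Pregnancy testing appears in three places:

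- **Screening, all groups.** Both event tables include hCG in the Visit 1 laboratory panel; the Table 1 row contains "lipid profile, TSH/ T4, A1c, NT-proBNP, hCG". The list of screening tests in the Study Protocol text omits hCG, but the two tables agree with each other.
- **Table 2, Group II.** The row "POC urine pregnancy test" is marked at Visits 4 and 5, the two PET days. It is blank at Visits 2 and 3, the two MRI days, on each of which β-OH-B or NaHCO3 is infused.
- **Myocardial Glucose Uptake section.** The text gives the occasion for that test: "Point-of-care urine pregnancy test will be done for women of reproductive age prior to injection of radioisotopes".

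Table 1 (Groups I and III) has no repeat-test row, and the Study Protocol's description of the MRI day mentions no pregnancy test.

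**The concern.** Pregnancy excludes a woman from any group, yet for Groups I and III it is checked once, at a visit that always precedes the infusion by at least a week. In those groups the infusion is the study intervention and there is no PET day. Group III, with the highest target (about +5.0 mmol/L), is among the groups never re-tested.

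A woman who conceives after screening, or whose pregnancy becomes detectable only afterwards, could be infused for 6 hours (3 hours in Group III) while meeting an exclusion criterion. Nothing in the visit schedule for that day would reveal it. What is at stake is participant safety and confirmation of eligibility at the time of exposure. No estimate, test or sample-size figure depends on it.

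**Working it through.** The plan states no figure on this point. The check compares the schedules with the text and adds up the visit windows.

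**1. Infusion visits and same-day tests**

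| Group | Scheduled infusion visits | With same-day test | Without |
|---|---|---|---|
| I | Visit 2 | 0 | 1 of 1 |
| III | Visit 2 | 0 | 1 of 1 |
| II | Visits 2, 3 (MRI); 4, 5 (PET) | 2 (Visits 4, 5) | 2 of 4 |

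**2. Age of the screening hCG at the first infusion**

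- By the text (Study Protocol: "Within 1-4 weeks after the screening visit, subjects will return"): 1 × 7 = 7 days to 4 × 7 = 28 days.
- By the tables (screening Day -30 to -7, MRI Study 1 Day 0-30): shortest 0 − (−7) = 7 days; longest 30 − (−30) = 60 days.

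Text and tables disagree on the upper limit. On either, the screening result is never same-day.

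**3. Age of the screening hCG at Group II MRI Study 2, default order**

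Table 2 places this visit at "Day 7-30 after MRI Study 1", which adds 7 to 30 days.

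- Text window plus table spacing: 7 + 7 = 14 to 28 + 30 = 58 days.
- Tables alone: 7 + 7 = 14 to 60 + 30 = 90 days.

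**4. If PET is done first**

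The Myocardial Glucose Uptake section allows this for Group II, depending on scanner availability. The last test would then be at the second PET study. No spacing is given for the reversed order. Assuming the same 7 to 30 days between visits, that test would be 7 to 30 days old at the first MRI infusion and 14 to 60 days old at the second. The MRI days would still have no test of their own.

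**5. Number of visits affected**

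- Proportion female: 39/78 = 0.5, assumed equal across groups.
- MRI-day infusions, taking one woman in each group: 1 (Group I) + 2 (Group II) + 1 (Group III) = 4.
- At 19 per group (Study Protocol): 19 × 0.5 × 4 = 38 visits in women.
- At 26 per group (Sample Size): 26 × 0.5 × 4 = 52 visits in women.

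Only women of reproductive age would be tested, and the documents do not give that share. Taking 0 to 20% purely as an assumption, the upper end is 0.20 × 38 = 7.6 or 0.20 × 52 = 10.4. The range is thus none to about 10 visits. These are visits without a same-day test, not expected pregnancies.

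**The case against.** The plan can be read as a coherent, risk-proportionate choice. Pregnancy is an eligibility criterion, and hCG checks it at screening in every group. A second test is added where radioisotopes are given, and MRI involves none. The Subjects paragraph does not promise verification at every visit, so the schedule does not contradict it. The exclusion follows directly after the sentence on MRI contraindications and gives no reason for itself. No fetal hazard of β-OH-B, NaHCO3 or MRI is named, and the target increments are described as within the range seen with SGLT2 inhibitors. The population has type 2 diabetes, NYHA Class II-III heart failure and a reduced ejection fraction, and the documents do not show that any enrolled woman would be of reproductive age.

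Much of this stands, and it rules out several stronger readings that a reader might infer:

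- **That the trial does no pregnancy testing in Groups I and III.** Both tables list hCG at screening.
- **That the exclusion exists to prevent exposure to the infusion, or that the infusion is known to be harmful in pregnancy.** The documents say neither.
- **That contraception or pregnancy-reporting rules are absent.** Consent pages were removed before review, so this cannot be judged.

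The objection does not remove the gap. The exclusion covers women who will never have a PET scan, and the documents offer no reassurance about the infusion in pregnancy. A screening test cannot detect a pregnancy that begins after it. Explaining why the urine test accompanies radioisotopes does not show that it is unnecessary before the infusions.

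**Conclusion.** The point holds as a modest one. Followed as written, the plan gives no same-day pregnancy test before any MRI-day infusion, and Groups I and III have none after screening. The table windows allow a screening result up to 60 days old at the first infusion and up to 90 days old at Group II's second MRI; using the text's screening-to-MRI interval, the limits are 28 and 58 days.

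The schedule finding rests on no assumption. Whether a same-day test is needed before these infusions is a safety judgement that the documents do not address. The number of women concerned is unknown and could be zero. This supports a recommendation to extend the test, and not a claim of internal contradiction or demonstrated hazard. The analysis, power and alpha are unaffected.

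**What to change.** Require the point-of-care urine pregnancy test already in use, for women of reproductive age, before every study infusion:

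- add a urine-test row to Table 1, marked at Visit 2;
- mark Visits 2 and 3 in the existing row of Table 2;
- add one sentence to the Study Protocol text stating the rule.

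Wording the rule by infusion rather than by visit also covers two exposures that are in neither table: the optional NaHCO3 control infusions in Groups I and III (Study Protocol), and the contingency 72-hour β-OH-B infusion (Expected Results).

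The cost is these edits and a small number of urine tests: none to about 10 for the scheduled MRI days under the assumed 0 to 20% share, plus any for the optional infusions. Visit timing, sample size and analysis do not change.

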glucose, FFA, lactate, pyruvate, glycerol, HCO3, insulin, glucagon, renin and aldosterone. Axial and sagittal localizer views, standard two-, three-, and four-chamber views, with 7 mm thick slices are obtained using gradient echo sequence (2.2 x 1.3 mm^2 pixel). Cine imaging with retrospective gaiting is used with a balanced steady-state free precision sequence (TR/TE = 2.44/1.22 ms). Acquisitions consist of 25-30 cardiac phases, matrix 224 x 288, FOV 336 x 430 mm^2, 1.5 x 1.5 mm^2 pixel area. Contiguous short-axis slices are acquired during repetitive breath-holds at expiration. Mitral inflow images are obtained using phase-contrast gradient-echo (PCGE) sequence with through-plane velocity encoding (Venc = 100 cm/s) at the mitral valve with flip angle = 10° and TR/TE = 5.8/3.6 ms. PCGE slice thickness was 8 mm with typical FOV = 228 x 430 mm^2, matrix = 192 x 102, producing 2.89 x 2.89 x 8.0 mm pixel volumes.

Following completion of the baseline MRI, subjects will be divided into three groups (19 subjects per group). Each group will receive a 6-hour (3-hour in group III) prime-continuous infusion of racemic  $\beta$ -OH-B (100 mg/mL solution; pH adjusted to 7.4) to increase the plasma  $\beta$ -OH-B concentration by ~0.5, ~2.0, and ~5.0 mmol/L (43,74).

GROUP I: Prime = 0.4 mg/kg.min for 20 minutes and constant rate = 0.2 mg/kg.min until study end

GROUP II: Prime = 1.5 mg/kg.min for 20 minutes and constant rate = 0.75 mg/kg.min until study end

GROUP III: Prime = 4.0 mg/kg.min for 20 minutes and constant rate = 2.0 mg/kg.min until study end

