These 3 infusion rates were chosen to cover the range of observed increments in plasma ketone concentrations in type 2 diabetic patients treated with a SGLT2 inhibitor: a  $\beta$ -OH-B increment of ~0.5 mmol/L typically is seen in diabetic individuals treated with an SGLT2 inhibitor, while a  $\beta$ -OH-B increment of 2-5 mmol/L is observed in ~5-10% of individuals (54-62). After 5 (or 2) hours of  $\beta$ -OH-B infusion, the cardiac MRI will be repeated. All baseline blood samples will be repeated at 360, 365, and 370 minutes (6 hours) or at 180, 185, and 190 minutes (3 hours) after the start of the  $\beta$ -OH-B infusion. Based upon prior studies from our group (42), we expect to reach steady state levels of  $\beta$ -OH-B in 60 minutes; this will be documented by measuring  $\beta$ -OH-B (and acetoacetate) levels every 30-60 minutes throughout the study. From the study of Gormesen et al (70), we know that 6 hours is sufficient to see a significant reduction (by 50%) in myocardial glucose uptake in normal-glucose-tolerant subjects. Blood glucose and electrolytes are monitored throughout the study with the instantaneous-result device (iSTAT Handheld Analyzer), and potassium supplement may be given before the start of the  $\beta$ -OH-B infusion to prevent decrease in blood potassium level. The investigator will decide to give 20-40mEq of KCL to subjects with initial potassium in the low limit of normal. The investigator will make this decision based on the risk of the subject to develop low serum potassium based on their medical history and renal function. The contraindication for KCL supplementation is elevated blood potassium. It is unlikely that diabetic patients w not taking an insulin secretagogue (i.e. sulfonylureas) will develop hypoglycemia.

Therefore, individuals with history of taking insulin secretagogues (i.e. sulfonylureas) will have hourly glucose monitoring during the  $\beta$ -OH-B infusion to ensure early detection of hypoglycemia. If at any time a subject develops any symptoms suggestive of hypoglycemia (i.e. anxiety, diaphoresis, hunger, weakness etc.) glucose will be measured immediately. If hypoglycemia occurs, we will treat subjects with 15 grams of rapid acting carbohydrates (i.e. juice), and re-check subject's blood glucose level in 15 minutes, and repeat if necessary, until normoglycemia has been reached.

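### On PET days the infusion lasts 380 minutes in the procedure text and 6 hours in Table 2, and neither covers the kidney and muscle scans, which end at 400 minutes

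*Combined protocol and SAP*

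**What the plan says.** Three places give the length of the Group II infusion.

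- **PET procedure (section on myocardial glucose uptake).** "At time zero a prime-continuous infusion of" beta-OH-B, with "prime = 1.5 mg/kg.min for 20 minutes", "is started and continued for 380 minutes". FDG is injected at 300 minutes and the cardiac scan follows. From 360 minutes, "two consecutive 20-minute dynamic scans of the abdominal and thigh area are performed to measure kidney and skeletal muscle glucose uptake". The repeat visit is the same except that NaHCO3 replaces beta-OH-B. Blood samples are scheduled about every 30 to 60 minutes while the infusion runs.
- **Table 2 (Group II events).** The row for beta-OH-B reads "6-hour prime-continuous infusion of" that solution and is marked for an MRI visit and a PET visit. The control row reads "6-hour prime-continuous infusion of NaHCO 3 (0.12 M solution" and is likewise marked for one MRI and one PET visit.
- **Study Protocol, Group II regimen.** "constant rate = 0.75 mg/kg.min until study end", with no minute given. This sits in the description of the MRI day.

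The Study Protocol also caps the infused volume at 300 mL and requires the beta-OH-B and NaHCO3 volumes to match.

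**The concern.** There are two linked defects. First, the text and the table give different infusion durations for the same visit, so staff following one would stop 20 minutes before staff following the other. If the two crossover days were run to different durations, the paired comparison would not be like with like. Second, neither duration reaches the end of the scans as timed.

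The late scans are there to measure kidney and skeletal muscle glucose uptake during hyperketonaemia, compared with the NaHCO3 day. A scan acquired after the infusion stops is no longer guaranteed to be at the ketone steady state that the plan intends. Because PET-day sampling is tied to the infusion, no ketone sample is guaranteed after it stops, so the data might not show how far levels had moved.

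**Working it through.** **Inputs**

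| Input | Value | Source |
|---|---|---|
| Infusion start | 0 min | PET procedure |
| Infusion end, text | 380 min | PET procedure |
| Infusion end, table | 6 h = 360 min | Table 2, both infusion rows |
| FDG injection | 300 min | PET procedure |
| Late scans | 2 × 20 min, consecutive, from 360 min | PET procedure |
| Group II rates | 1.5 mg/kg.min for 20 min, then 0.75 mg/kg.min | Study Protocol and PET procedure |
| Concentration | 100 mg/mL | Study Protocol |
| Volume limit | 300 mL | Study Protocol |

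**Step 1: scan times.** First late scan: 360 to 360 + 20 = 380. Second: 380 to 380 + 20 = 400. Allowing no time to reposition the subject, 400 minutes is the earliest possible end.

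**Step 2: scan minutes off infusion.** For each scan, minutes off infusion = max(0, scan end − max(scan start, infusion end)).

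| Infusion end | First late scan | Second late scan | Total of 40 | Cardiac window 300–360 |
|---|---|---|---|---|
| 360 (Table 2) | 20 | 20 | 40 | 0 |
| 380 (text) | 0 | 20 | 20 | 0 |
| 400 (380 counted after a 20-min prime) | 0 | 0 | 0 | 0 |

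For both late scans to lie within the infusion as timed, the infusion end and the scan end would have to coincide or be reversed. The gap is 400 − 380 = 20 minutes from the text and 400 − 360 = 40 minutes from Table 2.

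**Step 3: share of the FDG interval.** From injection to the last frame is 400 − 300 = 100 minutes. Of these, 20/100 = 20% (text) or 40/100 = 40% (Table 2) are off infusion. These are shares of time, not estimates of bias.

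**Step 4: volume, because a change of duration touches the cap.** Dose to time T = 1.5 × 20 + 0.75 × (T − 20) mg/kg; volume = dose / 100 mL/kg; weight at which the cap is reached = 300 / volume.

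| T (min) | Dose (mg/kg) | Volume (mL/kg) | Weight at 300 mL (kg) |
|---|---|---|---|
| 360 | 30 + 255 = 285 | 2.85 | 105.3 |
| 380 | 30 + 270 = 300 | 3.00 | 100.0 |
| 400 | 30 + 285 = 315 | 3.15 | 95.2 |

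The eligibility limit is BMI 38. At an assumed height of 1.65 m that is 38 × 1.65² = 103 kg, so weights in this range can occur.

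**The case against.** The strongest defence is that this is loose wording around measurements on which no stated objective rests. The specific aim covers LV function and myocardial glucose uptake. Neither Statistical Analysis nor Expected Results names a kidney or muscle endpoint, and the cardiac window is on infusion throughout. All of that stands, and it limits the importance of the point.

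It can also be argued that 380 minutes of constant infusion after a 20-minute prime ends at exactly 400, or that the until-study-end wording covers the scans. The first reading is strained, because the text dates the whole prime-continuous infusion from time zero. The second wording belongs to the MRI day and gives no minute. Both would still conflict with Table 2.

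A reader might infer more than the documents support:

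- **That the kidney and muscle differences are pulled toward zero.** The plan gives no rate of ketone decline after stopping and no expected kidney effect. Its Rationale says that beta-OH-B does not impair insulin-mediated glucose uptake in skeletal muscle. FDG uptake also reflects tracer delivered since 300 minutes, most of it on infusion. Attenuation is therefore not shown.
- **That the muscle scan is the one affected under the 380-minute text.** This rests only on the word order of abdomen then thigh; the scan order is not stated. One scan is off infusion in either order.
- **That MRI-day blood samples share the fault.** The plan says "All baseline blood samples will be repeated at 360, 365, and 370 minutes (6 hours) or at 180, 185, and 190 minutes (3 hours"). Tables 1 and 2 already label these samples as post-infusion, and the until-study-end wording may cover them. They are not part of this point.

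**Conclusion.** The inconsistency is real and minor. On the plain reading, the PET-day infusion is given as 380 minutes in one place and 360 in another, and the late scans end at 400. Following the text puts one of the two scans off infusion (20 of 40 minutes); following Table 2 puts both off (40 of 40). The myocardial endpoint is not touched.

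What is at risk is the interpretation of kidney and skeletal muscle uptake, and the comparability of the two crossover days if they are run to different durations. The size and direction of any bias cannot be derived from the documents. The conclusion assumes that the 380 minutes include the prime and that the two scans follow each other without a gap; any gap would lengthen the time off infusion.

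**What to change.** Reconcile the PET procedure, Table 2 and the Group II regimen in the Study Protocol so that one PET-day infusion duration is stated everywhere, is the same on the beta-OH-B and NaHCO3 days, and is consistent with the scan times. Which time moves is for the clinical team to decide, with a check against the 300 mL limit using the volumes in the working. If the times are left as they are, state the order of the two late scans, and label and analyse any scan acquired after the infusion stops as post-infusion.

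The cost is a wording change in three places and, at most, a shift of 20 to 40 minutes within an existing session. If the infusion is the part that moves, the volume check is a real constraint and not a formality: between 360 and 400 minutes, the weight at which the cap is reached falls from about 105 kg to about 95 kg.
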